- To analyze the proportion of participants which achieve $\geq 50\%$ of dietary and exercise goals.
- To explore the effect of CEDI on ChT toxicity and post-op complications

Study design:

- Open label randomized controlled trial

Patient recruitment:

Recruitment will be conducted at the Oncology center of Hospital Beatriz Ângelo and patient selection will be done during the weekly multidisciplinary meeting. Patients will be enrolled at diagnosis of upper GI cancer, namely esophagus, gastric and pancreatic, provided that they are eligible for neoadjuvant ChT and with age higher than 18 years and lower than 80 years. Sample size per group was calculated bearing in mind that according to data from the World Health Organization, 14% of Portuguese adults are compliant to moderate exercise, and in our study adherence will be set as a compliance higher than 50%. Considering a power of 0.80 and an α set at 0.05, 25 patients will be needed per group. Stratified block randomization will be

conducted to allocate 25 patients to standard care and 25 to CEDI. Stratification will be performed according to disease location. Randomization will be undertaken by a randomization list created by a web based randomization system.

Methods:

- ***Clinical data:***

Demographic data such as age, sex, education level, drinking and smoking habits, and clinical data as tumor site and histological type, ChT regimens, response and toxicity, will be retrieved from electronic records. Adverse effects will also be recorded, namely ChT toxicity graded according to NCI Common Toxicity Criteria, and post -operative complications with Clavien Dindo classification.

- ***Patient Generated Subjective Global Assessment (PG-SGA)***

PG-SGA is known to be an accurate tool for the identification of malnourished cancer patients (Ottery F. , 1996) (Ottery F. , 1994). In our study, PG-SGA assessment will be conducted by an experienced dietitian and patients will be classified as well nourished (SGA A), moderately or suspected of being malnourished (SGA B) or severely malnourished (SGA C).

- ***Anthropometric measures (AM):***

AM have been used consistently due to their non-invasive feature, portability, and low cost (Rosa G, 2008). AM such as weight and height will be obtained, and Body Mass Index will be calculated. All AM will be conducted according to previously established protocols (Rosa G, 2008).

- ***Body composition assessment***

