Dietary intake will be assessed with a Food frequency questionnaire and 24 recalls using a modified USDA five-pass method at diagnosis and every visit until surgery. The Semi-quantitative Food Frequency Questionnaire that will be used, was developed for the Portuguese population (Lopes, Aro, Azevedo, Ramos, & Barros, 2007) and is designed to evaluate usual dietary intake. This questionnaire includes 86 commonly-eaten food or drinks and participants were asked to estimate the amount and frequency of intake of each food/drink according to frequency and amount. Conversion of foodstuffs to nutrients will be conducted with software Food Processor Plus (ESHA Research, Salem, Oregon) which has been adapted to the Portuguese commonly-eaten food or drinks.

The 24h recall using a modified USDA five-pass method consists in 5 steps, the first is to list all foods consumed on the previous 24h. On the second step the interviewer asks about possible forgotten food items. In the third step the interviewer clarifies the time and occasion of the consumed foods. On the fourth step subject answers to standardized questions and clarifies portion size. In the last fifth step the interviewer seeks to obtain any additional information related to the foods consumed (Johnson & K, 2002). Conversion of foodstuffs to nutrients will be conducted with Sanut software which has been developed for the Portuguese population.

- ***Functional status assessment***

Performance Status will be assessed with Eastern Cooperative Oncology Group Performance Status scale (Oken, et al., 1982). According to these criteria patients are classified from grade 0

(fully active) to grade 4 (bedridden). Prior to initiation of ChT and before surgery, data on oxygen-consumption, optimum aerobic heart rate and ECG-recordings as well as 6 min walk test will be conducted. Also, hand held dynamometer assessing grip strength will be obtained. .

- ***Physical activity***

Physical activity will be assessed with the International Physical Activity questionnaire (Craig, Marshall, Sjostrom, Bauman, Booth, & Ainsworth, 2003). This questionnaire has been validated in several countries including Portugal, and is known to be a valid and reliable tool. Participants will be categorized has having a low, moderate or high physical activity according to the frequency, duration and intensity of physical activity on the previous seven days.

- ***Patient Reported Outcome Measures(PROMs)***

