- ***Adherence Assessment***

The primary outcome will be intervention adherence, in which patients consenting to engage in the intervention protocol will be evaluated. As a secondary outcome, we will assess to what extent participants achieve their dietary and exercise goals. Participants will be considered as adherent if they have met $\geq 50\%$ of their diet and exercise goals on the week preceding ChT. Also, follow up rates will be recorded, as well as comments on burden and acceptability of the intervention. Dropout rates and reasons for leaving the study will also be recorded. Contamination of the control arm will also be analyzed. Patients will be contacted every week by phone call or interview to assess adherence.

Statistical analysis:

Statistical analysis will be conducted for the primary and secondary outcome with an intention to treat and per protocol approach, respectively. Continuous variables will be described as mean, median and range, while categorical variables will be expressed as frequency and percentage. Differences in mean continuous variables will be analyzed by t-test or Mann Whitney U test as appropriate, according to variable's adjustment to a normal distribution. Shapiro-Wilk test will be used to test normality. Pearson or Spearman correlation analysis will be performed as appropriate to assess the association between continuous variables. Chi square test of independence or Fisher exact test will be used to assess the association between categorical variables.

Ethics:

The study protocol has been approved by the Scientific and Ethics Committee of Hospital Beatriz Ângelo in Loures, Portugal. Informed consent will be obtained from every patient.

Clinical data will be prospectively collected from electronic charts, however data will be coded in order to maintain anonymity.

References:

Bruera, E., Strasser, F., Palmer, J., Willey, J., Calder, K., Amyotte, G., et al. (s.d.). Effect of Fish Oil on Appetite and Other Symptoms in Patients With Advanced Cancer and Anorexia/Cachexia: A Double-Blind, Placebo-Controlled Study. *Journal of Clinical Oncology*, 21(1), 129-134.

Chu, M. P., Lieffers, J., Ghosh, S., Belch, A., Chua, N. S., Fontaine, A., et al. (2017). Skeletal muscle density is an independent predictor of diffuse large B-cell lymphoma outcomes treated with rituximab-based chemoimmunotherapy. *Journal of Cachexia, Sarcopenia and Muscle*, 8(2), 298-304.

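### Physical activity is planned only as low, moderate or high and would go to an unordered test; the weekly amount compared by ranks would use the same answers better, chiefly for the contamination analysis

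*Combined protocol and SAP*

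**What the plan says.** Under Methods, Physical activity, the International Physical Activity Questionnaire covers the previous seven days, and the form described is "Participants will be categorized has having a low, moderate or high physical activity according to the frequency, duration and intensity". No weekly total or other continuous score is mentioned, no reason is given for using three levels, and no assessment times are stated.

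Under Statistical analysis, "Chi square test of independence or Fisher exact test will be used to assess the association between categorical variables". Continuous variables go to a t-test or Mann-Whitney U test.

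Under Adherence Assessment, "Contamination of the control arm will also be analyzed", with neither a measure nor a test named. The supervised sessions and the home-exercise record are described under the intervention arm. Under the control arm, exercise may be advised where relevant, without a personalised programme. The Physical activity section speaks of participants and does not limit the questionnaire to one arm.

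**The concern.** Frequency, duration and intensity together give a weekly amount of activity. Reducing them to three levels sets aside differences within a level, and an unordered test then also ignores that high is more than moderate and moderate more than low. Patients starting chemotherapy may cluster in the lowest level, where a real increase could leave the label unchanged.

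What is at stake is the reading of contamination. Controls may receive exercise advice, so the plan is right to look at it. With 50 patients, an unremarkable three-by-two table could be taken to show that the arms did not separate when the same answers, used in full, would show that they did.

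**Working it through.** **The plan's own figure.** Inputs from Patient recruitment: "14% of Portuguese adults are compliant to moderate exercise"; "in our study adherence will be set as a compliance higher than 50" per cent; "Considering a power of 0.80 and an α set at 0.05, 25 patients will be needed per group". Take p1 = 0.14 and p2 = 0.50. The second is an assumed reading, since the text gives 50% as a threshold. Alpha is assumed two-sided.

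n per group = [z(0.975)·√(2p̄(1−p̄)) + z(0.80)·√(p1(1−p1) + p2(1−p2))]² / (p2−p1)², with p̄ = 0.32

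= [1.960·√0.4352 + 0.842·√0.3704]² / 0.36² = 3.26 / 0.1296 = 25.1, so 26. The arcsine version gives 24.3, so 25. Power at 25 per group is 0.798. The stated size reproduces, but it was set for adherence, not for the activity categories.

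**Inputs for the activity measure.** The plan will "conducted to allocate 25 patients to standard care and 25 to CEDI", so there are 25 per arm. The documents give no effect size, SD or category shares for the questionnaire, so these are assumptions:
- a normal latent activity score, shifted by d SD in the intervention arm;
- d = 0.8, or d = 1.08, the shift that moves 14% above a cut to 50%: z(0.86) − z(0.50) = 1.08 − 0;
- low/moderate/high cut points set by control-arm shares of 86/10/4%, 60/30/10% or 40/40/20%.

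**Method.** Simulation, 20,000 runs per setting, two-sided 0.05. Three analyses of the same data: Mann-Whitney on the full score (A), Mann-Whitney on the three ordered categories (B), and chi-square on the three categories with 2 df (C). Loss from categories = A − B; loss from ignoring order = B − C; total = A − C.

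| d | Control split, % | A | B | C | A − B | B − C | A − C |
|---|---|---|---|---|---|---|---|
| 0.8 | 86/10/4 | 0.770 | 0.552 | 0.430 | 0.218 | 0.122 | 0.340 |
| 0.8 | 60/30/10 | 0.770 | 0.688 | 0.581 | 0.082 | 0.107 | 0.189 |
| 0.8 | 40/40/20 | 0.770 | 0.700 | 0.597 | 0.070 | 0.103 | 0.173 |
| 1.08 | 86/10/4 | 0.950 | 0.829 | 0.735 | 0.121 | 0.094 | 0.215 |
| 1.08 | 60/30/10 | 0.950 | 0.914 | 0.853 | 0.036 | 0.061 | 0.097 |
| 1.08 | 40/40/20 | 0.950 | 0.914 | 0.849 | 0.036 | 0.065 | 0.101 |

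The total loss is 10 to 34 points. The categories account for about 3 to 22: the table's smallest value is 3.6, and a repeat run put B as high as 0.92, so 0.95 − 0.92 = 0.03. In the two more balanced splits more than half of the loss comes from ignoring order (for example 0.107/0.189 = 57%). In the 86/10/4 split the categories take the larger share (0.218/0.340 = 64%). The exact Fisher test in place of chi-square gives similar power: 0.420, 0.571 and 0.576 at d = 0.8, and 0.707, 0.849 and 0.848 at d = 1.08.

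**Sensitivity.** If 70% of controls report zero activity (86/10/4, d = 0.8), the ties lower A to about 0.66; against chi-square at 0.42 the gap is 24 points instead of 34. In the other direction, if 86/10/4 is the split of both arms combined, C falls to 0.233 at d = 0.8 and the loss is 0.770 − 0.233 = 54 points.

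**The case against.** The plan declares no arm comparison of physical activity. Its aims are completion of the intervention, attainment of goals, toxicity and post-operative complications; the primary outcome is adherence. The one announced use that may involve this questionnaire is contamination, which could be met by a descriptive report, and power is a weak yardstick for a description. This stands, and it limits the weight of the point. It does not remove it: if the two arms are set side by side, the amount says more than the label.

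A reader might infer that the recorded minutes are thrown away. The documents do not say so; they describe a categorisation and plan no other use. The Mann-Whitney test is already listed for continuous variables, so the gap is one derived variable.

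A reader might also put the whole 10 to 34 points down to the categories. The table does not support that: an ordered test on the same three levels recovers roughly 6 to 12 points.

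Nor is it certain that this is the only record of exercise behaviour in controls. The weekly contact to assess adherence names no arm. It names no instrument either, so the questionnaire remains the only named one not limited to the intervention arm.

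Finally, the model treats the levels as cuts of a single score, whereas the questionnaire classifies on three components, and every effect size and split is assumed. The figures are conditional on this.

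**Conclusion.** The point holds as a modest, inexpensive improvement. As written, the only described form of the activity measure is a three-level label, and the planned test for it ignores order. Under the assumptions above, this costs about 10 to 34 points of power against a rank test on the full amount: about 3 to 22 from the categories and the rest from the unordered test. Many patients at zero would reduce the gain; heavy clustering of both arms in the lowest level would raise the loss.

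The tempting stronger conclusion, that the trial is underpowered for its main question, does not follow. The primary outcome is intervention adherence, the 25 per group were set for that, and neither depends on the questionnaire's categories. The consequence is confined to the contamination analysis and to any comparison of activity between arms that the investigators choose to make.

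**What to change.** Under Physical activity, state that intensity-weighted minutes per week will be derived from the recorded frequency, duration and intensity for patients in both arms, and at which visits the questionnaire is given. Under Statistical analysis, state that this quantity will be compared between arms with the Mann-Whitney test already listed. Under Adherence Assessment, name the same quantity for the contamination analysis. Keep low, moderate and high as a descriptive table; if that table is tested, use an ordered test.

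The cost is a sentence or so in each place, with no new data. The small downside is that self-reported minutes are skewed, with extreme values and ties at zero. A rank test tolerates these with some loss of power.

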Quality of life questionnaires from the European Organization for Research and Treatment of Cancer (EORTC), specifically gastric, esophagus and pancreas modules, which have already been validated for the Portuguese population, will be used to asses Patient Reported Outcome Measures at the end of Chemotherapy treatment.

- ***Intervention arm-Combined Dietary and Exercise Intervention in the***

The intervention group will receive a supervised combined moderate aerobic and resistance training, once per week with duration of 40-60 min plus daily home exercise The exercise program will be planned by an exercise physiologist aiming at personalization of exercise according to patient's age and functional capacity.

Besides exercise, intervention group will receive a one-on-one nutritional counseling, by a Dietitian. In the first visit the dietary plan will be designed and oral nutritional supplements (Forticare®, Nutricia) will be recommended to meet 1.5g of protein/kg. Patients will be recommended to take one of the supplements after exercise. Also, in order to meet a calorie intake of 30kcal/kg, patients will be recommended to maintain a fat intake of 30% of total daily calories, where 20% will be supplied by olive oil. Written materials will be given to patients and caregivers, namely a dietary plan, standard menus, recipes, and standard portions information. Follow up visits will take place every time the patient is at the hospital to receive ChT .

Patients will be recommended to maintain the dietary plan and exercise during the whole ChT treatment plan. However, due to possible symptoms after ChT, namely nausea and vomitings, patients will be asked to intensify compliance on the week preceding ChT when there is a higher probability that patients are symptom free. Patients will be contacted twice a week by phone call or interview to provide motivation support and to assess if any diet or exercise

adjustment is needed in order to maximize adherence. Also an adhesion record will be provided to the patient for monitoring of adhesion to protein, olive oil, water, supplements intake as well as home exercise.

- ***Control arm- Standard care:***

Patients allocated to the control arm will receive standard care, in which patients will be referred to the dietitian only when the clinician feels there is a need for a dietary review. Whenever relevant, exercise will be recommended but without a personalized training program, which is our current practice.

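### Quality of life is measured only at the end of chemotherapy; a baseline form would let this small trial adjust for starting level, describe change and characterise dropouts at little cost

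*Combined protocol and SAP*

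**What the plan says.** All references are to the combined protocol and SAP.

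- **PROMs section.** The instruments are EORTC questionnaires, "specifically gastric, esophagus and pancreas modules", and they "will be used to asses Patient Reported Outcome Measures at the end of Chemotherapy treatment". That is the only time point given. The text available for this review contains no baseline or intermediate quality-of-life assessment. No scale of interest, SD or target difference is named.
- **Dietary Intake assessment.** Intake is recorded "at diagnosis and every visit until surgery".
- **Functional status assessment.** Oxygen consumption, the 6-minute walk and related tests are done once before chemotherapy and again before surgery.
- **Patient recruitment.** "Considering a power of 0.80 and an α set at 0.05, 25 patients will be needed per group". This rests on adherence, with a reference rate described as "14% of Portuguese adults are compliant to moderate exercise" and an adherence threshold of 50%. On balance between the arms: "Stratification will be performed according to disease location".
- **Statistical analysis.** Continuous variables are compared by t-test or Mann-Whitney test. No covariate-adjusted model is planned.
- **Aims and Adherence Assessment.** Quality of life is not among the general or specific aims, and it is not the primary or secondary outcome. Dropout and its reasons are to be recorded, but no dropout rate is assumed.

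**The concern.** The introduction gives better patient-reported outcomes, quality of life included, as part of the case for exercise, so readers will look at this result. With one measurement after treatment, three things are out of reach whatever model is used:

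- **Adjustment for starting level.** This is usually the strongest predictor of the later score and so the main source of extra precision in a small trial.
- **Description of change.** The trial could not say whether quality of life was preserved or lost during chemotherapy in either arm.
- **A check on missing forms.** A patient who leaves before the end of chemotherapy contributes no quality-of-life data, so the trial cannot show whether those patients started worse on this measure.

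Allocation is stratified by disease location only. Any chance difference between the arms in starting quality of life would therefore be neither visible nor correctable. A baseline that is not collected at the time cannot be recovered later.

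**Working it through.** **1. The plan's own figure.** Inputs from Patient recruitment: 14%, 50% (read as the target rate, an assumption), power 0.80, alpha 0.05 (taken as two-sided; the plan does not say). The pooled two-proportion formula without continuity correction has mean proportion 0.32:

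n = [1.96·√(2·0.32·0.68) + 0.842·√(0.14·0.86 + 0.50·0.50)]² / 0.36² = (1.293 + 0.512)² / 0.1296 ≈ 25.1, so 26 per arm.

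Power at 25 per arm is 0.798, and the arcsine version gives 24.3, so 25. The stated size is reproduced to within one patient. It was set for adherence, not for quality of life.

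**2. End-only comparison of quality of life.** The plan gives no SD, so results are in SD units. Assume all 25 per arm return a common score, two-sided 0.05, 80% power.

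- Normal approximation: (1.960 + 0.842)·√(2/25) = 2.802·0.283 = 0.79 SD.
- Noncentral t: 0.81 SD.

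**3. With a baseline and ANCOVA.** If the baseline-to-end correlation is r, the residual variance falls by the factor 1 − r². The detectable difference is then 0.809·√(1 − r²), and the equivalent end-only sample is 25/(1 − r²) per arm. The values of r are assumptions; the documents give none. Power is by normal approximation.

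| r (assumed) | √(1 − r²) | Detectable difference | Equivalent n per arm, end-only | Power for 0.5 SD (illustrative) |
|---|---|---|---|---|
| 0 (end-only) | 1.000 | 0.81 SD | 25 | 42% |
| 0.3 | 0.954 | 0.77 SD | 27 | 46% |
| 0.5 | 0.866 | 0.70 SD | 33 | 53% |
| 0.7 | 0.714 | 0.58 SD | 49 | 70% |

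At r = 0.5 the variance falls by 25%, worth 33% more patients. The degrees of freedom used for baseline and location change the detectable differences by no more than about 0.002 SD.

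**4. Change score instead of ANCOVA.** The variance factor is 2(1 − r), which is below 1 only when r exceeds 0.5. At r = 0.3 a change score is worse than end-only (0.94 against 0.79 SD, normal approximation). ANCOVA is the better use of a baseline.

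**5. Chance imbalance at baseline.** The standard error of the baseline difference is √(2/25) = 0.28 SD, ignoring any gain from stratification. The arms would differ by more than 0.3 SD with probability 29% and by more than 0.5 SD with probability 8%. An imbalance of 0.3 SD carries r × 0.3 SD into the end-of-chemotherapy difference: 0.09, 0.15 or 0.21 SD at r = 0.3, 0.5 or 0.7.

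**6. Less favourable conditions.** With 20 forms per arm (assumed), the end-only figure rises to 0.91 SD. If module scores can be compared only within a site, and the three sites split evenly at about 8 per arm (assumed), it is 1.51 SD end-only and 1.51·0.866 = 1.31 SD with ANCOVA at r = 0.5.

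**The case against.** A reader might infer that the end-only comparison is biased, or that it confuses a starting difference with an effect. The documents do not support that. Allocation is randomised, the standard error of an end-only test already includes chance baseline differences, and the type I error is kept. What is lost is precision, correction of whatever imbalance occurs in this one trial, and description.

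A reader might also infer that quality of life is the one measure left without a baseline. That is not supported either. Only dietary intake and the functional tests have a stated pre-treatment time. PG-SGA, anthropometry, CT, BIA, ECOG status and physical activity have no stated schedule.

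Four further objections stand, at least in part:

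- **Place in the trial.** No stated objective fails without a quality-of-life baseline, and a between-arm comparison is only implied by the general sentence on continuous variables. This limits how serious the point is.
- **Size of the gain.** At r = 0.3 it is slight (0.81 to 0.77 SD). Even at r = 0.5, power for a 0.5 SD difference is only 53%. A baseline does not make the trial adequately powered for moderate effects.
- **Different modules by site.** A location term shifts means; it does not turn different site modules into one scale.
- **Dropout.** A baseline describes patients with no final form but does not recover their outcome. Baseline diet and function, and the recorded reasons for leaving, already allow some description of them.

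None of this removes the inability to adjust for starting quality of life or to describe change, and no reason is given for omitting the baseline.

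**Conclusion.** The point holds as a worthwhile, inexpensive improvement to a supporting measure. It is not a flaw in the validity of the trial or in its primary result. As written, the plan can compare the arms on quality of life after chemotherapy, but with a detectable difference of about 0.81 SD. It cannot adjust for starting level, describe change, or show whether patients with no final form started worse on this measure. A baseline with ANCOVA would bring the figure to between 0.77 and 0.58 SD.

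These sizes rest on assumed correlations of 0.3 to 0.7, a two-sided 0.05 test, all 25 patients per arm returning forms, and a score common to all sites. Dropout or site-specific scores would make every figure larger. The loss of change and of baseline description depends on none of these assumptions.

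**What to change.** 1. **PROMs section.** Add the same EORTC questionnaires at the diagnosis assessment, before chemotherapy starts. The trial is open label and the measure is self-reported, so they should be completed before the patient's allocation is known.
2. **Statistical analysis section.** Name the scores that are common to all three disease sites. For those scores only, compare the arms at the end of chemotherapy by ANCOVA on the baseline score, with disease location (the stratification factor) in the model. Describe site-specific module scores by site, without pooling.
3. **Missing forms.** Report, by arm, the baseline scores of patients who have no end-of-chemotherapy form.

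The cost is one more questionnaire per patient, at an assessment where dietary intake is already collected, and a short amendment. No extra visit or procedure is needed. If enrolment has begun, the change can apply only to patients not yet randomised.

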It has also been hypothesized that exercise may inhibit tumor growth directly. In a recent experimental study, tumor bearing mice randomized to wheel running, showed a 60% reduction in tumor incidence across five different tumor models (Pedersen, et al.). Also, NK cell infiltration was significantly increased in tumors from running mice. Mechanistic analysis showed that NK cells were mobilized by epinephrine released during exercise, which resulted in a selective mobilization of IL-6 sensitive NK cells into the tumor. Another consequence of this mobilization of NK and other T cells, is to eventually sensitize and prime it to immunotherapy (Pedersen B. K., 2011).

Although an adequate dietary intake and exercise are suggested to improve body composition which may influence outcome, reported adherence to behavioral interventions has been showed to vary substantially. In a study that focused on evaluating the impact of exercise during and after treatments of recruited cancer patients from Radiation Oncology and Gynaecology department, adhesion to 3 and 6 month program of exercise was 93 and 91%, respectively (Grabenbauer, Grabenbauer, Lengenfelder, Grabenbauer, & Distel, 2016). Another

study aiming to explore the feasibility of dietary intervention focusing on a low-fat and high fruit and vegetable intake combined with moderate exercise in breast cancer patients, also found a high adherence (75%). However, according to a meta-analysis aiming at assessing adherence of colorectal adenoma patients to behavioral interventions such as diet and physical activity, a wide range of adherence was reported, 8 to 86 % and 13 to 47 %, respectively (McMahon, et al., 2015). Furthermore, in a feasibility study of exercise and diet interventions in pancreatic and lung cancer patients a suboptimal adhesion was reported, for exercise (60%), but especially for nutritional supplements (48%) (Solheim, et al., 2017).

Bearing in mind that adherence may be a limiting factor for randomized controlled trials investigating the effect of behavioral interventions, the purpose of our study is to conduct a study to investigate adherence of upper GI cancer patients to a combined exercise and dietary intervention.

General Aims:

- To study the adherence of upper GI cancer pts to a Combined Exercise and Diet Intervention (CEDI) during neoadjuvant chemotherapy.

Specific Aims:

- To determine the rate of completion of CEDI protocol.

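### Diet and exercise goal achievement is assigned to a per-protocol analysis only, in a set the plan does not define, although the outcome itself measures following the intervention

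*Combined protocol and SAP*

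**What the plan says.** The Statistical analysis section pairs outcomes with analysis sets in one sentence: "Statistical analysis will be conducted for the primary and secondary outcome with an intention to treat and per protocol approach, respectively". This is the only mention of a per-protocol approach. It gives no attendance, completion or exposure criterion and no list of deviations that would lead to exclusion.

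The Adherence Assessment section names the two outcomes. The primary: "The primary outcome will be intervention adherence, in which patients consenting to engage in the intervention protocol will be evaluated". The secondary: "As a secondary outcome, we will assess to what extent participants achieve their dietary and exercise goals". The next sentence gives a threshold, "Participants will be considered as adherent if they have met" at least 50% of their diet and exercise goals in the week before chemotherapy, without saying which of the two outcomes it serves. The same section provides for recording dropouts and their reasons and for weekly contact to assess adherence. It gives no rule for how dropouts count in the secondary outcome.

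**The concern.** A per-protocol set is ordinarily made up of patients who followed the protocol. Here the outcome is how far the patient followed it. If the set leaves out dropouts and non-compliers, membership depends on the outcome, and those left out are likely to be those with low goal achievement. The reported figure then describes patients who kept to CEDI. It does not describe how far patients offered CEDI reach the goals, which is the question a study of adherence has to answer.

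Because the set is undefined and the trial is open label, the choice of whom to exclude also stays open until goal achievement is known. No analysis of all allocated patients is planned for this outcome to set beside the per-protocol figure.

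**Working it through.** **The plan's own figure.** The Patient recruitment section states that "25 patients will be needed per group", from a 14% reference rate, α 0.05 and power 0.80. Assume that 50% is the expected rate in the CEDI arm and that the test is two-sided without continuity correction. The mean rate is then 0.32 and

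n = [1.96·√(2·0.32·0.68) + 0.842·√(0.14·0.86 + 0.50·0.50)]² / 0.36² ≈ 25.1, or 26 rounded up.

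Power at 25 per group is 0.798. The stated size reproduces to within one patient and is not in dispute. It is used below only as the denominator.

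**Where the 50% rule belongs.**
- *Primary (intention to treat).* The primary outcome is adherence, the rule says who is adherent, and the sample-size text says "in our study adherence will be set as a compliance higher than 50" per cent.
- *Secondary (per protocol).* The Specific Aims list "To determine the rate of completion of CEDI protocol" separately from "To analyze the proportion of participants which achieve" at least 50% of the goals, and the second aim matches the wording of the secondary outcome.

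Both readings are tenable. The extent of achievement is per protocol on either; the proportion reaching 50% is per protocol only on the second.

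**Extent of achievement (all inputs assumed).** Let m of 25 CEDI patients stop and be excluded, averaging s% of goals, while the rest average 60%. The all-CEDI mean is [(25 − m)·60 + m·s]/25. For m = 5 and s = 20 this is (20·60 + 5·20)/25 = 1300/25 = 52.0. The per-protocol mean is 60 throughout.

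| Stoppers' mean s | m = 2 | m = 5 | m = 8 |
|---|---|---|---|
| 20% | 56.8 (3.2 high) | 52.0 (8.0 high) | 47.2 (12.8 high) |
| 40% | 58.4 (1.6 high) | 56.0 (4.0 high) | 53.6 (6.4 high) |
| 60% | 60.0 (0) | 60.0 (0) | 60.0 (0) |

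Brackets give the excess of the per-protocol mean in percentage points.

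**Proportion reaching 50% (only if that rule is secondary; counts assumed).** Suppose 12 of 25 reach the threshold and every excluded patient is a non-achiever, which is the least favourable case:
- none excluded: 12/25 = 48%
- 2 excluded: 12/23 = 52%
- 5 excluded: 12/20 = 60%
- 8 excluded: 12/17 = 71%

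The exact 95% interval for 12/25 is 28% to 69%, so the shifts to 52% and 60% lie within sampling error. If exclusion is unrelated to achievement, nothing moves: 15/25 = 12/20 = 60%.

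**The case against.** The strongest reply is that the damage may be small. If the 50% rule defines the primary outcome, the main adherence figure is already under intention to treat and only a descriptive measure is left per protocol. That reading is reasonable, and it would make this a lesser point. The plan does not settle it.

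A second reply is that the bias is conditional: exclusions might be for ineligibility alone, in which case there is none. This stands. A reader might infer that the figure will certainly be inflated, or even that it must be 100% because the set will consist of patients who meet the adherence rule. The documents support neither inference, since they do not say how the set is formed.

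A third reply is that dropouts are recorded, so a reader could correct the figure. This is partly right. If all the excluded are dropouts counted as failures, 12/20 with 5 dropouts gives back 12/25. For the mean, the correction is only a range. A per-protocol mean of 60% in 20 of 25 fits an all-CEDI mean of 48% (20·60/25) to 60% if the excluded do no better than the rest, and up to 68% ((1200 + 500)/25) if they all meet every goal.

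Finally, per protocol is a fair question about those who kept to the programme. It is, as a supporting analysis.

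**Conclusion.** The concern holds in limited form and should be fixed. The text settles two things: the secondary outcome has a per-protocol analysis only, and the set is undefined. The direction of the likely error follows from the ordinary meaning of per protocol, and its size is not established. The illustrations (0 to about 13 points on the mean, 4 to 23 points on the proportion) rest entirely on assumed numbers of stoppers and assumed achievement. The adherence rates cited in the background come from other populations and do not supply these inputs.

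Two wider readings should not be drawn. The plan does not clearly put the main adherence proportion under per protocol. Nor does the sentence at issue assign chemotherapy toxicity or post-operative complications to it: these are exploratory aims with no stated analysis set.

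**What to change.** Amend the Statistical analysis section along these lines:

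- Goal achievement is analysed mainly in all patients randomised to CEDI, as allocated.
- Patients who stop the intervention or withdraw while chemotherapy continues count as not achieving the goals for the remaining pre-chemotherapy weeks.
- A rule for missing weekly records in patients who continue is fixed before analysis.
- A sensitivity analysis uses observed weeks only.
- The per-protocol result is a labelled supportive analysis, in a set defined in advance by criteria other than goal achievement.
- The plan states whether the 50% rule defines the primary or the secondary outcome.

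The cost is a short paragraph and two decisions: the missing-record rule and the place of the 50% rule. No new data are needed. Weekly adherence contacts, dropout reasons and the patient's adherence record are already planned, and chemotherapy details come from electronic records. The drawback is that the reported figure will probably be less favourable, and counting withdrawals as failures may understate achievement. The observed-weeks analysis shows how much depends on that choice.
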